    - Has treatment with axitinib been discontinued? (Yes/No)
      - If yes, specify:
        - End-of-treatment date
        - Reason for suspension of treatment (DP/Toxicity/Other, specify)
    - Risk criteria at discontinuation of treatment with axitinib

- 
- Time from first diagnosis to systemic treatment less than 1 year (Yes/No/Unknown)
    - ECOG/PS (current status) (Yes/No/Unknown)
    - LDH >1.5 x ULN (Yes/No/Unknown)
    - Haemoglobin < LLN (Yes/No/Unknown)
    - Corrected calcium >10 mg/dl (Yes/No/Unknown)
    - Presence of 2 or more metastatic sites (Yes/No/Unknown)
    - Platelets > ULN (Yes/No/Unknown)
    - Neutrophils > ULN (Yes/No/Unknown) (value)
  - Has there been disease progression? (No/Yes, specify date)
  - Best treatment response (CR, PR, SD, DP/Not evaluable).
    - Date of the best response obtained
  - Starting dose (5 mg/12 h; 2 mg/12 h; 3 mg/12 h; 7 mg/12 h; 10 mg/12 h)
  - Has the dose been modified? (Yes/No)
    - If yes, specify:
      - Increased/Reduced
      - Dose modification date
      - Reason for dose modification
      - New dose (5 mg/12 h; 2 mg/12 h; 3 mg/12 h; 7 mg/12 h; 10 mg/12 h; other, specify mg/h)
  - Adverse events
    - Adverse events (Anaemia; Asthenia; Fatigue; Diarrhoea; Dysphonia; Elevated ALT/GPT; Elevated AST/GOT; Elevated Bilirubin; Elevated Creatinine; Elevated Haemoglobin; Elevated Lipase; Hypercalcaemia; Hypertension; Hypocalcaemia; Hypophosphatemia; Hypothyroidism; Lymphopenia; Mucositis; Nausea; Neutropenia; Proteinuria; Rash; Hand-foot syndrome; Thrombocytopenia; Vomiting, Other, specify).
    - Worst grade according to CTCAE
    - Cycle in which the worst grade occurred
    - Related to treatment (Yes/No)
    - Serious AE? (Yes/No), if yes, specify
      - Reason (Results in death/ Is life threatening/ Leads to hospitalisation or prolongation of hospitalisation/ Causes persistent or significant disability or incapacity/ Causes a congenital anomaly or birth defect/ Is medically significant).
  - Subsequent treatments
    - Has the patient received any subsequent treatment? (Yes/No)
      - If yes, specify
        - Drug received
        - Starting dose
        - Treatment line
        - Start date

- End date
- Ongoing
- Best response attained (CR, PR, SD, DP/Not evaluable)
- Reason for discontinuation (DP/Toxicity/Other, specify)
- Vital status
  - Date of last follow-up
  - Status (Alive/Death)
    - If Death, specify
      - Date of death
      - Cause of death (DP, Other, specify)

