## 7 DEFINITION OF VARIABLES AND OBJECTIVES

In addition, the following variables will be calculated from the CRF data:

NOTE: In patients with dates after the date of the IC visit / signature, the date of the IC visit / signature has been considered as the date of the last check. Due to the retrospective nature of the study, no data can be collected after the patient was included in the IC study / signature.

- Age (years) of patient at time of visit= (Visit date – Date of birth) / 365.25
- Age (years) at first diagnosis= (Date of first diagnosis – Date of birth) / 365.25
- Age (years) at the initiation of axitinib= (start date of axitinib – Date of birth) / 365.25
- Number of metastatic locations = sum (Lymph nodes, CNS, Hepatic, Pulmonary, Bone, Other).
- • Neutrophil / lymphocyte ratio. It will be categorized as follows:  $\leq 3$ ,  $> 3$ . "Before the beginning of the first line" and "At the beginning of treatment with axitinib" will be analyzed. This ratio is not calculated on axitinib suspension because there is no current lymphocyte value data in that part of the CRF.
- Time (months) between first diagnosis and nephrectomy = (Date of nephrectomy – Date of first diagnosis) / 30.4375. A list with the information (site, patient, date of first diagnosis, date of nephrectomy and the calculated time) in cases in which the time is negative (with date of nephrectomy before or equal to date of first diagnosis) will be displayed, and these cases will not be included in the descriptive analysis
- Time (months) between first diagnosis and radiotherapy = (Date of radiotherapy – Date of first diagnosis) / 30.4375. A list with the information (site, patient, date of first diagnosis, date of radiotherapy and the calculated time) in cases in which the time is negative (with date of radiotherapy before or equal to date of first diagnosis) will be displayed, and these cases will not be included in the descriptive analysis.
- Time (months) between first diagnosis and 1st-line treatment = (Date of the initiation of 1st-line treatment – Date of first diagnosis) / 30.4375. A list with the information (site, patient, date of first diagnosis, date of 1st-line treatment and the calculated time) in cases in which the time is negative (with date of 1st-line treatment before or equal to date of first diagnosis) will be displayed, and these cases will not be included in the descriptive analysis

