- Duration (months) of previous 1st-line treatment = (Date of end of 1st-line treatment – Date of start of 1st-line treatment) / 30.4375. If a patient is detected in whom this duration cannot be calculated or a negative time is left, it will not be considered in the descriptive analysis, and a list will be shown with the information related to this calculation of said patient.

- 
- Pre-treatment of 1st line: a descriptive table with the collected drugs will be shown (if necessary, a list will be sent to the sponsor for the grouping of these drugs). In addition, the registered drugs will be grouped into three groups: Sunitinib, Other iTK, and Others, and the descriptive table will be included in the report.
  - Duration (months) of previous 2nd-line treatment =  
 $(\text{Date of end of 2nd-line treatment} - \text{Date of start of 2nd-line treatment}) / 30.4375$ . If a patient is detected in whom this duration cannot be calculated or a negative time is left, it will not be considered in the descriptive analysis, and a list will be shown with the information related to this calculation of said patient.
  - Duration (months) of previous 3rd-line treatment =  
 $(\text{Date of end of 3rd-line treatment} - \text{Date of start of 3rd-line treatment}) / 30.4375$ . If a patient is detected in whom this duration cannot be calculated or a negative time is left, it will not be considered in the descriptive analysis, and a list will be shown with the information related to this calculation of said patient.
  - Duration (months) of previous 4th-line treatment =  
 $(\text{Date of end of 4th-line treatment} - \text{Date of start of 4th-line treatment}) / 30.4375$ . If a patient is detected in whom this duration cannot be calculated or a negative time is left, it will not be considered in the descriptive analysis, and a list will be shown with the information related to this calculation of said patient.
  - Duration (months) of previous 5th-line treatment or further =  $(\text{Date of end of 5th-line treatment} - \text{Date of start of 5th-line treatment}) / 30.4375$ . It will be analyzed only if there is an adequate sample (enough high) of patients with 5th or later previous lines.
  - Duration (months) of treatment with axitinib =  
 $(\text{Date of end of axitinib treatment or of latest follow-up if not suspended} - \text{Date of start of axitinib treatment}) / 30.4375$
  - Time (months) to increase or Time (months) to reduction of axitinib dose =  

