- Duration of first-line treatment:([0-3] months, [3-6] months, [6-9] months, [9-12] months,  $\geq 12$  months).
- Duration of first-line treatment: ( $\leq 9$ months,  $>9$  months).
- Duration of first-line treatment: ( $\leq 12$ months,  $>12$  months).
- Duration of first-line TKi treatment: ([0-3] months, [3-6] months, [6-9] months, [9-12] months,  $\geq 12$  months).

It will be calculated the duration of the first line, if the drug was only a TKi.

- Duration of first-line TKi treatment: ( $\leq 9$ months,  $>9$  months).
- Duration of first-line TKi treatment: ( $\leq 12$ months,  $>12$  months).
- Duration of the first TKI treatment:( [0-3] months, [3-6] months, [6-9] months, [9-12] months,  $\geq 12$  months).

It will be calculated the duration of the first treatment with a TKi, in 1st or later line (always after axitinib).

- Patients treated with a TKi previous to axitinib other than first. It will be analysed the number of patients with a TKi previous to axitinib, different from the first TKi received.

It will be analysed the duration of this treatment.

- Best response with the TKI received in the first-line (CR, PR, SD, DP)
- Best response with a TKi previous to axitinib with a TKi other than first line (CR, PR, SD, PD).
- Best response with line prior to axitinib with a TKI if a line prior to axitinib other than the first one has been received (CR/PR, SD, DP).
- Number of metastatic locations (1, 2 and  $\geq 3$ ); See this definition in section 7 Definitions of variables and objectives.
- Site of metastases (CNS metastases [yes vs no]; lymph nodes [yes vs no]; lung [yes vs no]; liver [yes vs no]; bone [yes vs no]). In addition to showing the descriptive and comparative table of metastatic locations between groups, another similar table will be shown but with the categories “Hepatic” and “Bone” united in a single.
- Neutrophil/lymphocyte ratio  $\leq 3$  (yes vs no). See this definition in section 7 Definitions of variables and objectives. It will be analysed in all moments included in the study.
- Line of treatment in which it was received.

- 
- Presence of comorbidities.
  - Suspension of treatment.
  - Have you received any further treatment?
  - Has there been disease progression?
  - Best response to treatment (RC, RP, EE, PE).
  - Best response to treatment (RC / RP, EE, PE).
  - Duration of axitinib treatment.
  - Vital status

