## 7.2 SECONDARY OBJECTIVES

- Response to treatment with axitinib in the long-term responder group (defined as a PFS of at least 9 months with the drug). The "Best treatment response" variable from the "Treatment with axitinib" form will be analysed in this group of patients.
- Efficacy of axitinib by treatment line (second line treatment and further lines). Note: in treatments following axitinib, the "Date of progression" is not available, so times to progression will not be done.
  - o Treatment line in which axitinib is received (2,  $\geq 3$ ).

The following descriptive analyzes will be performed based on the treatment line on which axitinib has been received (2 vs.  $\geq 3$ ):

- o Best treatment response (CR, PR, SD, DP).
- o Duration of treatment.
- o Progression-free survival (this will not be performed for subsequent treatments).
- o Objective response rate (ORR) and clinical benefit (sum of CR, PR and SD).
- o Time to Progression (this will not be performed for subsequent treatments).
- o Overall Survival.
- Efficacy of axitinib per treatment line depending on the group (LR and Refractories)

A table will be displayed with the number of treatment line in which axitinib has been received in both groups of patients (2,  $\geq 3$ ). Depending on these groups (2,  $\geq 3$ ) the following analyzes will be performed in each of the groups (LR and PR):

- o Best treatment response (CR, PR, SD, DP).
- o Duration of treatment.
- o Progression-free survival
- o Objective response rate (ORR) and clinical benefit
- o Time to Progression
- o Overall Survival.

---

Likewise, a table will be shown with the number of patients with axitinib in the second line of treatment, and in  $\geq 3$  line in each group (long responders and refractories).

The following analyzes will be carried out by group (long responders / refractories):

- Best treatment response (CR, PR, SD, DP).
- Duration of treatment.
- Progression-free survival. PFS will be shown in all patients with axitinib in the second line of treatment, and PFS per group
- Objective response rate (ORR) and clinical benefit.
- Time to Progression
- Overall Survival. OS will be shown in all patients with axitinib in the second line of treatment, and OS per group
- Progression-free survival to sunitinib. PFS will be shown in all patients with axitinib in the second line of treatment, and PFS per group

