It will be calculated as follows: Progression Free Survival to sunitinib (SLP, in months) = (Date of Progression of the Disease to treatment with sunitinib - Start date of treatment with sunitinib) / 30,4375. If there is no progression, the case is censored in SLP (months) = (Start date of treatment with axitinib - Start date of treatment with sunitinib) / 30,4375.

- **Majority sequence**

The number of patients receiving the second-line treatment will be shown, following the sequence that is most observed in all the patients included (SUT-AXI-NIVO).

The following analyzes will be carried out by group (long responders / refractories):

- Best treatment response (CR, PR, SD, DP).
- Duration of treatment (months).
- Progression-free survival. PFS will be shown in all patients with sunitinib-axitinib sequence and PFS per group.
- Objective response rate (ORR) and clinical benefit.
- Time to Progression
- Overall Survival. OS will be shown in all patients with sunitinib-axitinib sequence and OS per group
- Overall Survival since the beginning of 1st line. OS will be shown in all patients with sunitinib-axitinib sequence and OS per group

It is defined as: Global Survival from the beginning of the first line (SG, in months) = (Exit date - Start date of first line treatment) / 30,4375. If there is no exitus the case is censored in Global Survival (SG, in months) = (Date of last control - Start date of the first treatment) / 30,4375.

- To describe the duration of treatment with axitinib. It will be described as it is described in section 7. Definition of variables and objectives
- To describe the percentage of patients who had increase the dose of axitinib above 5 mg twice daily. It will be described as it is described in section 7. Definition of variables and objectives
- To describe the percentage of patients who had reduce the dose of axitinib below 5 mg twice daily. It will be described as it is described in section 7. Definition of variables and objectives
- To describe the tolerability of axitinib (see point 9.2. Statistical analyses, Safety objectives).
- To describe the response to treatments received at progression. The treatments received will be described in cases of DP for first-line, 2nd line, etc.; that is, in treatments prior to axitinib.
- Overall survival based on post treatment
  - o Overall survival. The OS will be displayed according to having received further treatment (Yes vs. No).

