## **9 STATISTICAL METHODOLOGY AND STATISTICAL ANALYSIS**

### **9.1 STATISTICAL METHODOLOGY**

#### **Descriptive analysis:**

Continuous numerical variables will be described using the principal measurements of centralisation and dispersion (mean, median, standard deviation, minimum Min., maximum Max., 25th percentile [Q1], 75th percentile [Q3], N)." 95% confidence intervals shall be given for the main quantitative variables for results associated with the primary objective and the main secondary variables.

There will be two percentage columns in the descriptive analysis of the qualitative variables: the total (%) and valid (% valid) percentages, that is, the percentage of the sum of valid responses plus missing values and the percentage of the total valid responses.

For questions with more than one response option (multi-response questions), multiple response tables will be displayed. These tables will show two percentage columns:

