### Other analyses

A descriptive analysis will be performed of all variables that do not cover any of the above objectives, and which have been recorded in the CRF.

Observations to the descriptive analyzes:

- **SUBSEQUENT TREATMENTS:** The section on subsequent treatments will be analyzed in patients who have indicated suspension of axitinib treatment.

And in this set, the number of lines after axitinib registered will be obtained on the total number of patients and on patients with Have you received any subsequent treatment? = Yes. On this set of patients, post-axitinib treatments will also be analyzed as follows:

- **First post-axitinib treatment:** the drug received, and the best response achieved will be analyzed if the treatment continues. If it does not continue, the reason for the discontinuation will be analyzed (specifying if there are other reasons).

- **Second line and after suspension with axitinib:** a list with the registered data of these treatments will be shown.

- **DOSE MODIFICATION:** It will be described how many patients have modified doses and how many modifications have been registered. In patients with modification, the following elements will be described:

- **Type of modification** (the variables included in the CRD will be analyzed. This analysis should not be confused with the definition included in section 7 definition of variables and objectives of this document).

- **The changes registered** will be ordered in order of occurrence (1st modification, 2nd modification ... until the last one), and for each order the following will be described: the type of modification, the new dose and the reasons for modification.

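### Axitinib duration is cut at latest follow-up for patients still on drug but summarised as if complete, so its mean is too low whenever anyone is still being treated

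*SAP*

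**What the plan says.** SAP section 7 defines axitinib duration in months as "Date of end of axitinib treatment or of latest follow-up if not suspended" minus the start date, divided by 30.4375. The note opening that section fixes the last usable date at inclusion or consent, because "no data can be collected after the patient was included in the IC study / signature".

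Section 7 also defines PFS, time to progression and two versions of overall survival. Each comes with a sentence saying when the case is censored. PFS on sunitinib (7.2) has one too. Axitinib duration does not.

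Duration is then used in several places:

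- **Overall:** a named secondary objective, where the SAP says only "To describe the duration of treatment with axitinib. It will be described as it is described in section 7".
- **By response group:** "Duration of axitinib treatment" is in the 7.1 list analysed for association with the two groups, and duration appears again by group in 7.2.
- **By line (2 versus 3 or later):** 7.2 says "The following descriptive analyzes will be performed based on the treatment line on which axitinib has been received", and duration of treatment is in the list.
- **In subsets:** the sunitinib-axitinib majority sequence and the subpopulation of special interest (7.2).

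The general rule in 9.1 is "Continuous numerical variables will be described using the principal measurements of centralisation and dispersion", meaning mean, median, standard deviation, quartiles and range. Section 9.1 assigns Kaplan-Meier to survival analyses, and the efficacy variables to be compared between groups in 9.2 do not include duration.

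**The concern.** The plan expects some patients to be still on treatment. The CRF asks whether axitinib was discontinued, yes or no, and 9.2 says "The section on subsequent treatments will be analyzed in patients who have indicated suspension of axitinib treatment", which presupposes patients without suspension. Living patients may be enrolled. A patient who is progression-free beyond 9 months and still on drug at inclusion qualifies as a long responder through the censored PFS definition. For that patient the duration formula returns time so far, and the plain summaries treat it as a finished course.

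Refractory patients have already progressed, so the shortening falls mainly on long responders, the group the study is about. Three things are at stake: the reported mean duration, which has no other estimate in the plan; the size of the difference between response groups; and the comparison by line, which can be distorted if the share still on drug differs between lines.

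**Working it through.** The plan states no expected duration, so there is no figure to reproduce. The check asks how far the plain summaries move as the share of long responders still on drug, c, rises.

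**Inputs from the documents.** About 60 patients (Protocol 8.5, SAP 2.1) at about 2:1 long responders to refractory (Protocol abstract, study population), so about 40 and 20. Long responders are described as treated for at least 9 months (Protocol 8.2, SAP 2.1).

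**Assumptions.** Time on drug in long responders is T = 9 + R, with R exponential with median 6.7 months, so its mean is m = 6.7 / ln 2 = 9.67. Censoring is independent of R. Refractory patients average 2 months and have all stopped. The documents do not give c; it is varied from 0 to 40%.

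**Mean.** For exponential R and any independent censoring time C, counted like R from month 9, E[min(R, C)] = m × P(R ≤ C) = m(1 − c). The plain mean is therefore 9 + 9.67(1 − c) = 18.67 − 9.67c, whatever the censoring pattern.

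**Median.** This depends on the pattern. The true value is 9 + 6.7 = 15.7. The table gives averages over simulated samples of 40 with censoring spread over the whole period.

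| c | plain mean (months) | plain median, spread-out censoring (months) |
|---|---|---|
| 0% | 18.7 | 15.7 (true value) |
| 10% | 17.7 | 15.1 |
| 20% | 16.7 | 14.5 |
| 30% | 15.8 | 13.8 |
| 40% | 14.8 | 13.1 |

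If all censoring is late, the simulated plain median stays at 15.7 to 15.8, so it is not biased.

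**Sensitivity to m.** A residual median of 4 months (m = 5.77) gives a bias in the mean of −0.6 at c = 10% and −1.2 at 20%. A residual median of 12 months (m = 17.31) gives −1.7 and −3.5. A separate run with m = 12 gave the same picture: true mean 21.0, with plain means of 19.7 at 10% and 18.6 at 20%.

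**Contrast by response group.** The difference in means is 18.67 − 9.67c − 2, which is 16.7, 15.7 and 14.7 months at c = 0, 10 and 20%. It shrinks but does not change direction. In the m = 12 run, with refractory durations assumed between 1 and 4 months, the Mann-Whitney p-value stayed below 1e-9 even with 50% still on drug.

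**Whole sample.** (40 × (18.67 − 9.67c) + 20 × 2) / 60 gives 13.1, 12.5 and 11.8 months at c = 0, 10 and 20%.

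**By line.** Suppose true durations are the same in both lines, each line has the 2:1 mix, and 10% versus 30% of long responders are still on drug. The plain means then differ by (2/3) × 9.67 × (0.30 − 0.10) = 1.3 months from censoring alone.

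**Does Kaplan-Meier repair it?** With censoring declared, the simulated Kaplan-Meier median is 15.8 to 15.9 months at c = 10 to 40% under exponential censoring, against a true 15.7.

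**Deaths on drug.** The CRF item reads "Reason for suspension of treatment (DP/Toxicity/Other, specify", so death is not a listed reason and a death on drug could be recorded as not suspended. If 10% or 20% of treatment ends were such deaths and were censored, the Kaplan-Meier median would rise to 16.5–16.6 or 17.6. Counted as events, they leave it at 15.6 to 15.8.

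**The case against.** The strongest reply is that the definition is coherent. Time to stopping, or to last follow-up if not stopped, is observed exposure, and the stated aim is only to describe duration in an exploratory study. A reader might infer that the formula itself is wrong. The documents do not support that: what is missing is a censoring statement or a label.

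The plain-summary reading is also partly inferred. Section 7.2 places PFS and overall survival under the same descriptive analyses, so the word descriptive does not by itself exclude Kaplan-Meier. The inference rests on section 7, which is silent for duration where the neighbouring endpoints are explicit, and on the secondary objective pointing back to that section.

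The share still on drug may be small, since Protocol 9.1 expects many patients to have died before inclusion. Suspension is tabulated by group (7.1), and withdrawal follows duration in the axitinib part of the table list (section 10). The cut-off will therefore be visible by group, though not clearly by line. Visibility does not correct the mean.

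A reader might also infer that the main findings are at risk. They are not. Response groups are defined from PFS and best response, and the regression is limited to factors before axitinib.

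Finally, 7.1 plans a descriptive mean and confidence interval for PFS in long responders. One might conclude that PFS is analysed without regard to censoring. That goes too far: PFS has a censoring rule, it is compared between groups under 9.2, and Kaplan-Meier is the survival method in 9.1. Only that one table is affected.

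**Conclusion.** The point holds as a defect of reporting and estimation in a secondary objective. The plain mean understates duration whenever c is above zero; the median does so only if some censoring precedes it. Under the base assumptions the loss in the long-responder mean is about 1.0 month at 10% still on drug and 1.9 months at 20%, and nothing at 0%.

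These sizes rest on an assumed exponential residual, independent censoring, an unknown c and a 9-month floor on treatment. The floor follows the population description; the operative criterion is PFS of at least 9 months, so a long responder could have stopped the drug earlier. The direction of the bias in the mean does not depend on the particular values.

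The correction is worth making because the plan has no other estimate of duration and the comparison by line can be misleading. The long-responder PFS table is a minor instance of the same problem.

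**What to change.** In SAP section 7 and under the duration objective in 7.2, state that:

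- Axitinib duration is summarised by Kaplan-Meier as in 9.1: median, 95% confidence interval, number of events and number censored.
- The event is end of axitinib or death on axitinib, whichever comes first. Only patients alive and still on axitinib are censored, at latest follow-up.
- This applies overall, by line, by response group, in the majority-sequence subset and in the subpopulation of special interest.
- Any plain mean or median is labelled observed exposure to date, with the number still on treatment. The summed duration of subsequent treatments, built the same way in section 7, gets the same label.
- The contrast of duration by response group stays descriptive. A log-rank test adds nothing, because the groups are defined largely by PFS.

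In 7.1, footnote the mean PFS of long responders with the number censored and refer to the planned Kaplan-Meier PFS.

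The cost is SAP wording and slightly more analysis work. The CRF already records discontinuation, end-of-treatment date, vital status, date of death and date of last follow-up, so no new data are needed.
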